2.2 STUDY OBJECTIVES

Primary objective - To Characterize the UC Patient Group Treated with Tofacitinib.

- a. Patient demographics at tofacitinib treatment initiation: age, gender, weight, height, smoking status, body mass index (BMI), treating hospital.
- b. Disease characteristics: age at diagnosis, duration of disease, and extent of colonic involvement according to the Montreal classification: E1 (ulcerative proctitis), E2 (left sided, distal colitis), E3 (pancolitis).
- c. Disease severity as assessed by Mayo score and f-calpro at the initiation of tofacitinib use.
- d. Laboratory results for biochemical inflammatory markers plasma C-reactive protein (P-CRP), blood thrombocytes (B-thromb), plasma albumin (P-alb), blood leukocytes (B-leuk), blood lymphocytes (B-ly), blood neutrophiles (B-neutr), blood hemoglobin (B-hb) and f-calpro at the start of tofacitinib treatment (baseline data).

e. Endoscopic findings including histology at the start of tofacitinib treatment (baseline data).

Secondary objective 1 - To Assess the Real-world Effectiveness of Tofacitinib.

- a. Proportion of patients who are taking to facitinib at week 8, 16, 24 and 52.
- b. To assess rates of clinical remission defined by a full or partial Mayo score at week 8, 16, 24 and 52.
- c. To assess rates of clinical response defined by a full or partial Mayo score at week 8, 16, 24 and 52.
 - note, objectives b and c were formulated as "rates" in the protocol, whereas the goal is to report "proportion of patients" as in majority of the other effectiveness objectives
- d. Proportion of patients in steroid-free clinical remission at weeks 8, 16, 24, and 52 as defined by full or partial Mayo who did not require any corticosteroid treatment during the period ≥4 weeks prior to the visit (for all patients and for those treated with corticosteroids at baseline).
- e. Proportion of patients reaching clinical response as defined by full or partial Mayo score at week 8, 16, 24 and 52.
 - note, objectives c and e were unintentional duplicates left in the protocol development
- f. Time to response as assessed by a decrease as defined by full or partial Mayo score.
- g. Proportion of responders defined by a f-calpro reduction of $\geq 50\%$, $\geq 75\%$ or $\geq 90\%$ at week 8, 16, 24 and 52 compared to baseline.
- h. Proportion of patients reaching f-calpro below 250 mg/kg at week 8, 16, 24 and 52 of those that had f-calprotectin above 250 mg/kg at baseline and change from baseline in f-calpro at week 8, 16, 24 and 52.
- i. Proportion of patients in sustained remission (pMayo and full Mayo score) from week 8 to week 16, 24 and 52.
- j. Proportion of patients in sustained remission (pMayo and full Mayo score) from week 16 to week 24 and 52.

[figure not shown]
k. Proportion of patients in sustained steroid free remission (pMayo and full Mayo score) at week 16 to 24 and 52 (for all patients and for those treated with corticosteroids at baseline).

- *l.* Change in partial and full Mayo score at weeks 8/16/24/52.
- m. Proportion of patients in sustained endoscopic remission (sub score = 0), mucosal healing (sub score 0-1) or endoscopic response (sub score reduction from baseline of ≥ 1) from week 8 to week 16, 24 and 52.
- n. Proportion of patients in physician assessed histological remission determined as inactive disease, or normal histology, and change from baseline in histology assessment (0= normal histology, I= inactive disease and 2 = active disease) at week 8/16/24/52.
- o. Proportion of patients in sustained steroid free remission (pMayo and full Mayo score) (for all patients and for those treated with corticosteroids at baseline) and endoscopic remission (sub score = 0), mucosal healing (sub score 0-1) or endoscopic response (sub score reduction from baseline of ≥ 1) from week 8 to week 16, 24 and 52.
- p. Comparison of response and remission (pMayo and full Mayo score) based on the extent of colonic involvement.
- q. Proportion of patients with corticosteroid tapering at weeks 8/16/24/52 and their tapering rates and doses.
 - note after further discussions, the data required for objective q might not be present in the available medical records and/or prescriptions
- r. Proportion of patients with improvement in stool frequency sub score of 1 or more points and change from baseline in stool frequency sub score at week 8, 16, 24 and 52.
- s. Proportion of patients with improvement in rectal bleeding subscore of 1 or more points and change from baseline in rectal bleeding subscore at week 8, 16, 24 and 52.
- t. Proportion of patients reaching normal P-CRP levels (below 4mg/L) and change from baseline in P-CRP levels at week 8/16/24/52.
- u. Proportion of patients reaching normal B-hb levels (men: 134–167 g/L, women: 117–155 g/L) and change from baseline in B-hb levels at week 8/16/24/52.
- v. Proportion of patients reaching normal B-leuk levels (3.4-8.2 x 10^9 /L) and change from baseline in B-leuk levels at week 8/16/24/52.

- w. Proportion of patients reaching normal B-Thromb (150–360 x 10^9 /L) and change from baseline in B-Thromb levels at week 8/16/24/52.
- x. Proportion of patients reaching normal B-ly (1.3-3.6x 10⁹/L) and change from baseline in B-ly levels at week 8/16/24/52.
- y. Proportion of patients reaching normal B-neutr (1.5-6.7 x $10^9/L$) and change from baseline in B-neutr levels at week 8/16/24/52.
- z. Proportion of patients reaching normal P-alb (18-39 years: 36-48 g/L, 40-69 years: 36-45 g/L, 70 years and over: 34-45 g/L) and change from baseline in P-alb levels at week 8/16/24/52.
- aa. Proportion of patients with extended to facitinib induction dose (additional 8 weeks with 10mg).
- bb. Real-world dosing of tofacitinib, e.g., usage of a higher dose (10 mg) as maintenance therapy.
- cc. Survival without drug discontinuation, colectomy or UC-related hospitalization (using time to event analysis).

Secondary objective 2 - To Assess Treatment Lines Prior to Tofacitinib Treatment.

a. Number and type of previous UC treatments.

3 HYPOTHESES AND DECISION RULES

There is no a priori hypotheses to be tested. All analyses are descriptive in nature, and there is no comparison between groups.

3.1 STATISTICAL HYPOTHESES

There is no a priori hypotheses to be tested. All analyses are descriptive in nature, and there is no comparison between groups.

3.2 STATISTICAL DECISION RULES

The alpha level will be 0.05, 2-sided. No adjustments for multiple comparisons will be made.

4 ANALYSIS SETS/POPULATIONS

4.1 FULL ANALYSIS SET

Full analysis set includes all patients fulfilling inclusion criteria, and not excluded due to exclusion criteria.

- 1. Xeljanz® (tofacitinib) usage for ulcerative colitis.
- 2. Diagnosis of ulcerative colitis (ICD-10: K51.0, K51.1, K51.2, K51.3, K51.5, K51.8, K51.9) between January 2010 and December 2021 (incident or prevalent).

Patients will be excluded if:

- 1. Age <18 years at the start of tofacitinib use.
- 2. Use of tofacitinib before reimbursement (01 Mar 2019).
- 3. < 8 weeks of treatment with to facitinib at the start of data mining.
- 4. History of panproctocolectomy, IPAA or ileostomy.

4.2 SAFETY ANALYSIS SET

NA

4.3 OTHER ANALYSIS SET

NA

4.4 SUBGROUPS

5 ENDPOINTS AND COVARIATES

5.1 EFFICACY/EFFECTIVENESS ENDPOINT(S)

- Proportion of patients who are taking to facitinib at week 8, 16, 24 and 52
- Rate of clinical remission
- Rate of clinical response
- Proportion of patients in steroid-free clinical remission
- Proportion of patients reaching clinical response
- Time to response
- Proportion of responders defined by a f-calpro reduction of $\geq 50\%$, $\geq 75\%$ or $\geq 90\%$
- Proportion of patients reaching f-calpro below 250 mg/kg of those that had f-calprotectin above 250 mg/kg at baseline
 - o change from baseline in f-calpro
- Proportion of patients in sustained remission (pMayo and full Mayo score) from week 8 to week 16, 24 and 52
- Proportion of patients in sustained remission (pMayo and full Mayo score) from week 16 to week 24 and 52
- Proportion of patients in sustained steroid free remission (pMayo and full Mayo score) at week 16 to 24 and 52 (for all patients and for those treated with corticosteroids at baseline).
- Change in partial and full Mayo score
- Proportion of patients in sustained endoscopic remission (sub score = 0), mucosal healing (sub score 0-1) or endoscopic response (sub score reduction from baseline of ≥1) from week 8 to week 16, 24 and 52
- Proportion of patients in physician assessed histological remission determined as inactive disease
 - o change from baseline in histology assessment

- Proportion of patients in sustained steroid free remission (pMayo and full Mayo score) (for all patients and for those treated with corticosteroids at baseline) and endoscopic remission (sub score = 0), mucosal healing (sub score 0-1) or endoscopic response (sub score reduction from baseline of ≥1) from week 8 to week 16, 24 and 52
- Proportion of patients with corticosteroid tapering
 - o tapering rates and doses
- Proportion of patients with improvement in stool frequency sub score of 1 or more points
 - o change from baseline in stool frequency sub score
- Proportion of patients with improvement in rectal bleeding sub score of 1 or more points
 - o change from baseline in rectal bleeding sub score
- Proportion of patients reaching normal P-CRP/B-hb/B-leuk/B-Thromb/B-ly/B-neutr/P-alb levels
 - o and change from baseline levels
- Proportion of patients reaching normal B-hb levels
 - o change from baseline in B-hb levels
- Proportion of patients with extended to facitinib induction dose (additional 8 weeks with 10mg).
- Real-world dosing of to facitinib
- Survival without drug discontinuation, colectomy or UC-related hospitalization

5.2 SAFETY ENDPOINTS

NA

5.3 OTHER ENDPOINTS

NA

5.4 COVARIATES

See table 1 for variables to be collected with their operational definitions.

6 HANDLING OF MISSING VALUES

No imputation for missing values will be performed. Proportion of missing values will be reported where appropriate.

7 STATISTICAL METHODOLOGY AND STATISTICAL ANALYSES

7.1 STATISTICAL METHODS

General:

Means, medians, and standard deviations, and 25% and 75% quartiles will be provided for continuous variables when performing descriptive analysis of continuous data. Numbers and percentages will be provided for dichotomous and polychotomous variables when performing descriptive analysis of categorical data.

Serial measures collected will be handled by "carry forward imputation", i.e. the latest value will be assumed unchanged until otherwise proven. Thus for each timepoint, the latest available measure will be used. Patients will be censored from the study post the last available contact/data entry. Missing values will not be imputed.

An unadjusted Kaplan Meier curve will be drawn to illustrate time-to-event and to estimate medians for time-to-event outcomes.

All data analysis will be executed using R, a language and environment for statistical computing and graphics, version 4.0.3 or later in Rstudio environment.

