2.1 STUDY DESIGN

The target population for this study is adult ulcerative colitis patients who were prescribed to facitinib. Estimated number of patients in this study is 100-150, with the aim of covering all ulcerative colitis patients in Finland treated with to facitinib. The main inclusion criteria are a diagnosis of ulcerative colitis (ICD-10: K51) between January 2010 and December 2021 and treatment with to facitinib. The main exclusion criteria are age under 18 years, use of to facitinib before national reimbursement decision on 01 March 2019 and history of panproctocolectomy, ileal pouch-anal anastomosis (IPAA) or ileostomy.

The data collected has been generated as part of standard clinical care, treatment, and follow-up of ulcerative colitis patients. In accordance with the Finnish Act on Secondary Use of Health and Social Data 552/2019 (in Finnish: Laki sosiaali- ja terveystietojen toissijaisesta käytöstä), health registry data can be processed in scientific studies without patient consent. The purpose of this act is to establish conditions for the effective and secure processing of, and access to, personal health and social data for certain secondary purposes, such as research and statistics, innovation and development, knowledge management, teaching and authority planning. Thus, the Secondary Act creates a clear legal basis for the use of such registered data for research and innovation related to, for example, the health and well-being of citizens, the prevention of disease and the development of new treatment methods. This relatively new legislation is also a welcome unification of the fragmented Finnish national rules regarding the use of healthcare and social welfare data. In addition, it takes into consideration current data protection requirements.

The data will be collected by data miners in all hospital districts across Finland and entered into an electronic data mining tool (eDMT) which will be designed for the study in collaboration with Finnish clinicians. The data will be used to investigate and describe the patient population, treatment strategies and disease development.

Figure 1. Study Timeline

FPFV= First patient first visit, LPLV= Last patient last visit.

Please note that dates are subject to change depending on how long permit process with Findata takes.

Study population

The study is a descriptive single cohort study. Patients must meet all of the following inclusion criteria to be eligible for inclusion in the study:

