Fecal calprotectin	Primary objective 7.2.1.d, Secondary objectives 7.3.1.g and 7.3.1.h.	mg/kg
Plasma CRP	Primary objective 7.2.1.d Secondary objective 7.3.1.t	mg/L
Blood hemoglobin	Primary objective 7.2.1.d, Secondary objective 7.3.1.u	g/L
Blood leukocytes	Primary objective 7.2.1.d Secondary objective 7.3.1.v	cells/L
Blood thrombocytes	Primary objective 7.2.1.d Secondary objective 7.3.1.w	cells/L
Blood lymphocytes	Primary objective 7.2.1.d Secondary objective 7.3.1.x	cells/L
Blood neutrophiles	Primary objective 7.2.1.d Secondary objective 7.3.1.y	cells/L
Plasma albumin	Primary objective 7.2.1.d Secondary objective 7.3.1.z	g/L
Tofacitinib dose	Secondary objectives 7.3.1.a, 7.3.1.aa and 7.3.1.bb	mg*times/per day or "not on treatment"
Colectomies	Secondary objective 7.3.1.cc	Date
Type of healthcare contact	Secondary objective 7.3.1.cc	outpatient visit, remote contact, emergency visit or hospitalization

Variable	Role	Operational definition
Prior IBD treatments	Secondary objective 7.3.2	Yes/no (For each treatment)
 corticosteroids 5-aminosalicylic acid (5-ASA) azathioprine 6-mercaptopurine methotrexate cyclosporine ustekinumab vedolizumab adalimumab infliximab golimumab 		
Concomitant medications o corticosteroids o 5-ASA	Secondary objective 7.3.1.q,	product & dose
Extraintestinal manifestations: arthralgia, arthritis, sacroiliitis, pyoderma gangrenosum, erythema nodosum, primary sclerosing cholangitis, uveitis, ankylosing spondylitis, aphthous stomatitis, psoriasis	CCI	Yes/no per pre-specified list
Prior diagnoses	CCI	Yes/no per pre-specified list
Death date or lost to follow up	Used to define end of follow up	Date

Further operational definitions from the collected data include:

Active disease:

• An endoscopic Mayo sub-score of ≥ 2 or fecal-calprotectin (f-calpro) > 250 mg/kg.

Clinical response:

• A full Mayo score decrease of ≥ 3 points and a decrease of $\geq 30\%$ from baseline, with a decrease of ≥ 1 point on the rectal bleeding subscore or an absolute rectal bleeding score of ≤ 1 .

• A partial Mayo score (ie, Mayo score without endoscopic assessment) decrease of ≥2 points and reduction of at least 25% in partial Mayo (pMayo) score from baseline with an accompanying decrease in rectal bleeding sub score of ≥1 point or absolute rectal bleeding sub score of ≤1.

Clinical remission:

- A full Mayo score of ≤ 2 points with no individual sub score exceeding 1 point, with rectal bleeding sub-score of 0.

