7.2 STATISTICAL ANALYSES

Primary objectives a-e:

Describe the patient population at the baseline (initiation of tofacitinib), using the data collected. For each continuous variables (age, BMI, age at diagnosis, duration of disease, laboratory measures), provide the mean, median, sd, 25%Q and 75%Q values. For categorical variables (sex, smoking status, extent of colonic involvement, disease severity, endoscopic findings), report the number of patients, and proportion. Report proportion of missing values if present.

Secondary objective - Assess the Real-world Effectiveness of Tofacitinib

Secondary objective a:

For each patient, define the "on treatment" as Yes/No based on the latest available dose (at each timepoint 8, 16, 24 and 52 weeks). Patients marked with "not on treatment" prior to timepoint will be regarded as discontinued.

Report the proportion of patients on treatment, not censored at each timepoint.

Secondary objectives b, c, d, e, g, n:

For each patient, define the fulfilment of the remission/response criteria as Yes/No based on the latest available data (at each timepoint 8, 16, 24 and 52 weeks).

Report the proportion of patients on fulfilling the response/remission criteria, not censored at each timepoint.

Secondary objective f:

Define the time of response for each patient as first ever data-entry that fulfils response criteria. Fit competing-risk time-to-event model to the data, with time-to-event defined as time from index until response (event) or discontinuation (competing event), or end of data collection (censoring event).

Assess the cumulative incidence as function of time for both types of events. Illustrate the Aalen-Johansen state probabilities of multistate model.

Secondary objective h:

Select only patients with baseline f-calprotectin above 250 mg/kg at baseline. For each subsequent f-calprotectin measure, define below 250 mg/kg as Yes/No variable. Additionally, estimate the absolute delta change per baseline value.

For each timepoint (week 8, 16, 24 and 52), report the proportion of patients on fulfilling the <250mg/kg criteria, and summary statistics (mean, median, sd, 25%Q and 75%Q) of delta change, among patients not censored at each timepoint.

Secondary objectives i, j, k, m, o:

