Select only patients that were on remission/steroid free remission at the timepoints. For each patient, define the fulfilment of the remission/response criteria as Yes/No based on the latest available data (at each timepoint 16, 24 and 52 weeks). Report the proportion of patients on fulfilling the remission criteria, not censored at each timepoint.

Secondary objective l:

For each available Mayo score (full or partial), estimate the absolute delta change from baseline value. For each timepoint (week 8, 16, 24 and 52), report the summary statistics (mean, median, sd, 25%Q and 75%Q) of delta change, among patients not censored at each timepoint.

Secondary objective p:

Perform analyses described in secondary objective b and c, stratified by the extent of colonic involvement

Secondary objective q:

For each patient, define the corticosteroid tapering as Yes/No based on the latest available data (at each timepoint 8, 16, 24 and 52 weeks). Additionally, define the tapering rates and doses based on latest available data.

For each timepoint (week 8, 16, 24 and 52), report the proportion of patients that had corticosteroid tapered, among patients not censored at each timepoint. Additionally,

report summary statistics (mean, median, sd, 25%Q and 75%Q) of tapering rates and doses among patients that had corticosteroids tapered.

Secondary objectives r and s:

For each patient, define the fulfilment of the improvement criteria as Yes/No based on the latest available data (at each timepoint 8, 16, 24 and 52 weeks). Additionally, estimate the absolute delta change per baseline value

Report the proportion of patients on fulfilling the response/remission criteria, report the summary statistics (mean, median, sd, 25%Q and 75%Q) of delta change, among patients not censored at each timepoint.

Secondary objectives t-z:

For each subsequent laboratory measure, define "normal-level" as Yes/No variable. Additionally, estimate the absolute delta change per baseline value. For each timepoint (week 8, 16, 24 and 52), report the proportion of patients on fulfilling the "normal-level" criteria and summary statistics (mean, median, sd, 25%Q and 75%Q) of delta change, among patients not censored at each timepoint.

Secondary objective aa:

Report the proportion of patients that received extended induction

Secondary objective bb:

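### SAP 7.1 carries the latest value to every timepoint with no visit window, age limit or bar on baseline, so week-8 response and sustained remission can rest on old measurements

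*SAP*

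**What the plan says.** SAP 7.1 sets one general rule for serial measures: "the latest value will be assumed unchanged until otherwise proven. Thus for each timepoint, the latest available measure will be used". SAP 7.2 then applies it by objective.

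- **Objectives b, c, d, e, g, n** (remission, response, f-calpro reduction, histology): each patient is scored Yes or No "based on the latest available data (at each timepoint 8, 16, 24 and 52 weeks"). Objectives r and s use the same basis, and p repeats b and c by disease extent.
- **Objectives i, j, k, m, o** (sustained outcomes): the instruction is "Select only patients that were on remission/steroid free remission at the timepoints". Those patients are then re-scored "based on the latest available data (at each timepoint 16, 24 and 52 weeks").
- **Objective h**: "For each subsequent f-calprotectin measure, define below 250 mg/kg as Yes/No variable". Objectives t to z are worded in parallel, which points to post-baseline values.

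The only limit on carrying is censoring: "Patients will be censored from the study post the last available contact/data entry". Table 1 (SAP 2.1) lists the contact types as "outpatient visit, remote contact, emergency visit or hospitalization".

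The measurements were not scheduled by the study: "The data collected has been generated as part of standard clinical care, treatment, and follow-up of ulcerative colitis patients". Protocol 8.9 expects partly incomplete data and warns that score components may be unavailable.

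SAP 6, and the end of the same paragraph in 7.1, state that missing values are not imputed, although 7.1 itself calls the carry-forward rule imputation.

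**The concern.** With charts from routine care, many patients will have no Mayo score, endoscopy or calprotectin near a nominal week. The rule fills such a gap with whatever came before, however old, and the effect depends on the type of outcome.

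- **Response and change.** Response needs a fall from baseline, so a carried baseline can only be a No and its change is zero.
- **Remission and histology at a timepoint.** These are absolute states. Inclusion does not require active disease, so a carried baseline may score either way and the direction of bias is not fixed.
- **Sustained outcomes.** Patients are chosen because they were in remission at the starting week. With no newer measure, the qualifying value is used again, so lack of follow-up is counted as success. A later phone contact or an unrelated laboratory entry keeps the patient in the week-52 denominator.

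Most effectiveness rows of SAP Table 3 depend on this rule. Part of the apparent course from week 8 to week 52 could reflect when patients were measured and not how they fared. Table 3 has a single row for the number of patients per timepoint, so it does not separate observed from carried values.

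**Working it through.** The plan has no sample size calculation or expected rate (protocol 8.5), so there is no stated figure to reproduce. The check has two parts.

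**Which limits exist**

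| Possible limit | Found in the documents? |
|---|---|
| Window around weeks 8, 16, 24, 52 | No |
| Maximum age of a carried value | No |
| Post-baseline values only | Implied for h and t to z; not for b, c, d, e, g, n, r, s; unclear for l |
| New measurement needed for sustained outcomes | No |
| End of carrying | Censoring at last contact or data entry, which limits follow-up but not the age of a measure |

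A value used at week 52 can therefore be 52 weeks old, or older if the baseline measure predates the index date.

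**How large the effect could be (illustration)**

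The only input from the documents is N = 100 to 150 (protocol 8.5). The true rates and the unmeasured shares below are assumptions. Being measured is taken as unrelated to the true course.

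*Week-8 response.* Let p be the true response and q the share with no measure between baseline and day 56, all scored No. Scored response = p × (1 − q). With p = 50%:

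- q = 10%: 0.50 × 0.90 = 45%
- q = 25%: 0.50 × 0.75 = 37.5%
- q = 50%: 0.50 × 0.50 = 25%

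Mean change from baseline shrinks by the same factor (1 − q). For p from 40% to 60% and q from 10% to 40%, the bias p × q runs from −4 to −24 points.

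*Against sampling error.* The 95% half-width at 50% is 1.96 × √(0.25/N): 9.8 points for N = 100 and 8.0 points for N = 150. With p = 50%, the bias equals this at q = 0.098/0.50 = 19.6% and q = 0.080/0.50 = 16.0%.

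*Sustained remission.* Let r be the true sustained share and s the share of selected, uncensored patients with no new measure, all scored Yes. Scored share = s + (1 − s) × r. With r = 60%:

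- s = 10%: 0.10 + 0.90 × 0.60 = 64%
- s = 25%: 0.25 + 0.75 × 0.60 = 70%
- s = 50%: 0.50 + 0.50 × 0.60 = 80%

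For r from 40% to 60% and s from 10% to 50%, the bias s × (1 − r) runs from +4 to +30 points.

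**The case against.** The best reply concerns week 8. SAP 7.1 speaks of serial measures and ends by ruling out imputation, as does SAP 6. A patient with a baseline value alone arguably has no series and would be missing at week 8, not a non-responder. That reading is possible, but the SAP does not state it, and two programmers could produce different tables. It also does nothing for the sustained outcomes, where an earlier post-baseline value exists and is reused.

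Other points have some force:

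- Objective l refers to each available Mayo score, so its exposure to a carried baseline is less certain than for c, e, g, r and s.
- The half-width comparison uses the whole cohort. With an assumed 60 evaluable patients the half-width is 1.96 × √(0.25/60) = 12.7 points, and the break-even q is 0.127/0.50, about 25%.
- Windows reduce denominators, and protocol 8.6 bars export of groups under 5 patients, so some sustained full-Mayo or endoscopic cells may not be reportable.
- SAP 6 promises the proportion missing where appropriate. Once an old value has been carried, however, the timepoint no longer looks missing.
- The outcomes are secondary and descriptive, and the rule is openly pre-specified. That limits the severity, but these proportions are the effectiveness results that will be read.

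**Conclusion.** The point holds and should be fixed. The carry-forward rule is a working instruction, not an omitted detail. Followed literally, it biases week-8 response and change toward zero and sustained remission upward. For h and t to z the problem is confined to stale later values. The carry-forward rule does not affect the primary objective, time to response (f) or the composite time-to-event outcome (cc).

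Confidence is high that the limits are absent and that the direction is as described for response and sustained outcomes. The week-8 effect rests on reading the carry-forward sentence as covering baseline. The actual size is unknown. The illustrations assume that measurement is unrelated to outcome and that the unmeasured group has no interim value.

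**What to change.** In SAP 7.1, for disease-activity and laboratory outcomes:

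1. Use the observed post-baseline value nearest the nominal week within pre-specified half-open windows, with a rule for ties. One example is week 8: 4 to <12; week 16: 12 to <20; week 24: 20 to <32; week 52: 40 to <64. This example leaves weeks 32 to <40 unused; the study team should choose the bounds and state any gap.
2. Do not use a baseline value at any post-baseline timepoint.
3. For i, j, k, m and o, require a new measurement in the later window before scoring the outcome as sustained.
4. Show the number assessed in each row of Table 3.
5. Keep carry-forward for treatment-state records (tofacitinib and corticosteroid). Elsewhere, use it only as a labelled sensitivity analysis.
6. Reword SAP 6 and 7.1 so that one rule governs a timepoint with no measurement.

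A repeated-measures model on observed values, already foreseen in protocol 8.7, is an optional addition.

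The cost is SAP text and a revised derivation script, with no new data. Denominators will fall, missingness will be more visible, and some cells may drop below the export limit of 5. Being assessed within a window may itself depend on disease course. State this as a limitation; the carry-forward sensitivity analysis will show how much the choice matters.
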